9.3. Recording and reporting of SAEs, SARs AND SUSARs

All AEs will be recorded on the AE Log in the eCRF. Details of AEs will be recorded in the medical record. AEs will be assessed for severity by the PI. AEs will be recorded from the time a participant consents to join the trial until the participant's last trial visit. Any SUSAR, that the investigator becomes aware of, will be reported to the Sponsor irrespective of how long after IMP administration the reaction has occurred.

Assessment of severity of AEs:

Mild: An event that is easily tolerated by the participant, causing minimal discomfort, and not interfering with everyday activities.

Moderate: An event that is sufficiently discomforting to interfere with normal everyday activities.

Severe: An event that prevents normal everyday activities.

An AE may be classified as a SAE or AR.

Participants with unresolved AEs/SAEs at end of trial will be followed up until 30 days after participant's last visit. SUSARS will be followed until resolution, where a participant agrees to this.

The CI, PI or delegate will ask about the occurrence of AEs and hospitalisations at every visit during the trial. SAEs will be submitted on an SAE form to the Sponsor Pharmacovigilance Section via the online Tayside Pharmacovigilance System within 24 hours of becoming aware of the SAE. Site PIs will also notify the CI when submitting an SAE.

The evaluation of expectedness will be made based on the knowledge of the reaction and the RSI see Section 9.4. The Sponsor will make the definitive assessment on expectedness for the purposes of SUSAR reporting.

The Sponsor is responsible for reporting SUSARs to the Competent Authority, and the REC. Fatal or life-threatening SUSARs will be reported within 7 days and non-fatal and non-life threatening SUSARs within 15 days.

Reporting of safety data to the funders will be as detailed in the funding agreement.

9.4. Reference Safety Information, open treatment arms

The current version, of the RSI will be held in the TMF - specifically in Pharmacy Site File, Investigator Site File (ISF) and Sponsor File. The RSI will be reviewed at least annually and where there have been any changes to the Reference Safety Information which may impact on the trial the protocol will be reviewed and a substantial amendment submitted for regulatory approvals.

	Treatment	Reference Safety Information
Arm 2	Disulfiram	Summary of Product Characteristics, Section 4.8
Arm 3	Dipyridamole	Summary of Product Characteristics, Section 4.8
Arm 4:	Doxycycline	Summary of Product Characteristics, Section 4.8

Mitigation of risks is detailed in Appendix 1.

9.5. Responsibilities

CI/PI or delegated staff:

- Checking for AEs and ARs at all visits.

CI/PI or medically qualified delegate:

- Confirmation of eligibility criteria.
- Using medical judgement in assigning seriousness, causality and whether the event/reaction was related.
- Ensuring that all SAEs are recorded and reported to the sponsor within 24 hours of becoming aware of the event and provide further follow-up information as soon as available.

CI:

- Central data collection of AEs, ARs, SAEs, SARs and SUSARs according to the trial protocol onto a database.
- Ensuring that AEs and ARs are recorded and reported to the sponsor in line with the requirements of the protocol.
- Clinical oversight of trial participant safety, including an ongoing review of the risk/benefit.
- Immediate review of all SUSARs.
- Assigning Medical Dictionary for Regulatory Activities (MedDRA) or Body System coding to all SAEs and SARs.
- Periodically reviewing overall safety data to determine patterns and trends of events, or to identify safety issues, which would not be apparent on an individual case basis.
- Preparing the clinical sections and final sign-off of the Development Safety Update Report.
- Reporting safety information to funder as per contract.

Sponsor (UoD/NHS Tayside):

- Expedited reporting of SUSARs to the MHRA and REC within required timelines.
- Checking for (annually) and notifying PIs of updates to the Reference Safety Information for the trial.
- Preparing standard tables and other relevant information for the DSUR in collaboration with the CI and ensuring timely submission to the MHRA and REC.

Trial Steering Committee (TSC):

In accordance with the TSC Charter, the TSC will periodically consider recommendations from the DMC following their review of safety data and make decisions on early termination or continuation of recruitment to individual treatment arms and the overall trial.

Data Monitoring Committee (DMC):

In accordance with the DMC Charter, the DMC will periodically review overall safety data to determine patterns and trends of events, and identify potential safety issues, making recommendations to the TSC.

9.6. Notification of deaths

All deaths occurring during the trial, will be reported to the sponsor irrespective of whether the death is related to disease progression, the trial drug or an unrelated event. Deaths will be reported to Sponsor as SAEs as per Section 9.3.

9.7. Pregnancy reporting

Pregnancy itself is not considered an AE or SAE, unless there is a congenital abnormality or birth defect. Any unexpected pregnancy occurring during the trial and the outcome of the pregnancy, will be recorded on a TASC Pregnancy Notification Form, and submitted to the Sponsor Pharmacovigilance Section within 24 hours of becoming aware of the pregnancy and the outcome of the pregnancy. The pregnancy will be followed up until the end of the pregnancy. If the trial participant is a male, informed consent for follow up will be sought from his female partner.

9.8. Overdose

An overdose with associated AEs is recorded as the AE diagnosis/symptoms on the relevant AE section in the eCRF. Any dose administered other than prescribed dose for that participant will be reported to the Sponsor as a protocol breach.

If an overdose of trial drug occurs during the trial, then the Investigator or other site personnel will inform the appropriate sponsor representatives immediately, or no later than 24 hours after becoming aware of it. The designated sponsor representative will work with the Investigator to ensure that all relevant information is provided to the sponsor's Pharmacovigilance Committee.

	Treatment	Definition	Treatment
--	------------------	-------------------	------------------

Arm 2	Disulfiram	Exceeding the trial dose of 400mg per day.	Treatment should be symptomatic, and observation is recommended. Supportive therapy should be available, and measures may be necessary to counteract hypotension. Gastric lavage and/or activated charcoal may be considered in cases of disulfiram overdose. Severe vomiting might occur requiring administration of intravenous fluids.
Arm 3	Dipyridamole	Exceeding the trial dose of 400mg per day	Symptomatic therapy is recommended. Administration of xanthine derivatives (e.g. aminophylline) may reverse the haemodynamic effects of dipyridamole overdose. ECG monitoring is advised in such a situation.
Arm 4:	Doxycycline	Exceeding the trial dose of 100mg per day	Discontinue medication. Gastric lavage plus appropriate supportive treatment may be indicated.

9.9. Reporting urgent safety measures

The PI or other trial physician will take appropriate immediate urgent safety measures to protect the participants against any immediate hazard to their health or safety. The MHRA, REC and Sponsor will be notified in writing within three days.

9.10. The type and duration of the follow-up of participants after adverse reactions.

All ARs will be recorded as per section 9.3. Where ARs occur, assessment of clinical condition and appropriate treatment will be instigated by a delegated doctor and will continue until the symptoms resolve or the condition stabilises.

9.11. Development safety update reports

The DSUR will be prepared jointly by the Sponsor Pharmacovigilance Section and CI and submitted by the Sponsor to the MHRA on the anniversary of date of Clinical Trial Authorisation.

The DSUR and reports of SUSARs will be sent to REC by the Sponsor Pharmacovigilance Section. Any other safety reports, for example, reports of a DMC, will be sent by the CI to REC, with a Safety Report Form, and to the Sponsor.

10. STATISTICS AND DATA ANALYSIS

10.1. Sample size calculation

Given the nature of the trial, there is no overall sample size target, but the numbers of participants required for each treatment arm are:

	Treatment	n	Open/closed to recruitment
Arm 1	Usual care	Randomisation will continue to end of trial	Open
Arm 2	Disulfiram	42	Open
Arm 3	Dipyridamole	42	Open
Arm 4	Doxycycline	42	Open

Sample size calculations have been performed using the “Superpower” package in R version 4.2.1 and verified using simulations.

The primary endpoint is sputum NE at day 28. The standard deviation of log₁₀-transformed NE is estimated to be 0.5, using unpublished data from the ORBIT4 trial. A “moderate” standardised difference (Cohen, 1988) of 0.5 between the control and each treatment arm is targeted, which equates to a log₁₀-difference of 0.25, i.e. a reduction in NE of approximately 44% vs control after 28 days of active treatment. The DPP1 inhibitor Brensocatib achieved >90% reduction in NE, so the targeted difference is realistic.

Aiming to recruit the number of participants per treatment arm as above (to allow for up to 10% dropout), with concurrent equal randomisation to the shared control arm, the trial would have >80% power to detect such a difference at the 1-sided 10% significance level. This assumes adjustment for up to 4 covariates in the ANCOVA model, with a modest R² value of approx. 0.1. In reality, the R² value should be larger than this (based on ORBIT-4), so power should be closer to 90% (see Table 10.1.1) (Haworth et al. 2019).

Table 10.1.1. Power, given R² value of covariates, to detect a standardised difference in log₁₀-transformed NE at day 28 of 0.5 between each treatment arm and the shared control at the 1-sided 10% significance level.

R ² value of covariates (with up to 4 covariates)	Power
0.1	81.8%
0.2	85.1%
0.3	88.5%
0.4	91.9%

The design uses the rationale of randomised phase II screening designs in oncology (Rubinstein et al. 2005). By setting the type I error rate to 10% (higher than the conventional 5% for phase III trials but widely accepted in phase II) and targeting a moderate treatment effect size, the required sample size is restricted while maintaining good power. This allows us to quickly and efficiently evaluate multiple treatment options, screening out those that appear suboptimal, and taking forward any showing a sufficiently promising efficacy signal for confirmation in a larger randomised trial.

The analysis of each treatment arm will be performed separately. Treatment arm participants will only be compared to contemporaneously recruited control arm participants. Type I error rate is controlled at 10% for each pairwise comparison.

To aid recruitment, after completing the 56 day follow-up period, patients may be rescreened and re-randomized if they are willing to participate in the trial again. Re-randomisation will be performed independently, in the same way as for initial randomisations. (Kahan et al. 2015). There may be an increase in power using this approach, but with few patients expected to opt for re-randomisation, and multiple active arms decreasing the likelihood of re-randomisation to the same pairwise comparison, any benefit is expected to be small.

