6.3. Open treatment arm specific exclusion criteria

6.3.1. Arm 2: Disulfiram

- Currently on Disulfiram (patients should have a washout period of at least 30 days from last dose if they have previously received this medication)
- Hypersensitivity to Disulfiram
- Participant, or investigator objects to randomisation to Disulfiram
- Does not agree to cease consumption of alcohol during intervention and for 14 days following treatment discontinuation
- Chronic liver disease
- Alanine transaminase (ALT)>135 U/L at screening,
- Bilirubin >30 umol/L at screening.
- Uncompensated cardiac failure
- Coronary artery disease (diagnosis of stable or unstable angina, previous myocardial infarction)
- Previous history of stroke or transient ischaemic attack
- Uncontrolled hypertension
- Hereditary problems of galactose intolerance, total lactase deficiency or glucose-galactose malabsorption
- Recent psychiatric exacerbation
- Any significant acute or chronic psychiatric condition, including severe personality disorder, psychotic disorder or suicide risk.
- Hypothyroidism
- Porphyria

- Diabetes Mellitus
- Epilepsy

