7.3. Randomisation scheme

Participants will be randomised equally to any open arms they are eligible for. Participants will be allocated to an arm using a minimisation algorithm, with factors for centre, *Pseudomonas aeruginosa* infection recorded in the last 2 years and long-term use of macrolides.

Randomisation will initially open with a control arm and 3 treatment arms. When a treatment arm has recruited to its target, randomisation to that arm will be closed. When a new treatment arm is added, randomisation to that arm will be opened for all participants meeting the eligibility criteria for that arm.

Participants who have completed 56 days of follow-up (end of trial) may be rescreened and re-randomized if they are willing to participate in the trial again. Participants will receive a new copy of the current PIS, will be asked to complete a new Informed Consent Form, be given a new, unique participant identification number and eligibility will be rechecked prior to randomisation. All trial activities will be carried out as per protocol. Re-randomisation will be performed in the same way as for initial randomisations. Patients can be randomised a maximum of three times (i.e. initial randomisation and two re-randomisations).

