8.6. Drug supply and storage, open treatment arms

Where a site has difficulty obtaining the supply of medication for any of the treatment arms, the site will continue to recruit and randomise participants between the available treatment arms and usual care at that site.

	Treatment	Supply	Storage
Arm 2	Disulfiram	Generic drug, procured through site NHS pharmacy	As per summary of product characteristics (SmPC) conditions
Arm 3	Dipyridamole	Generic drug, procured through site NHS pharmacy	As per SmPC conditions
Arm 4	Doxycycline	Generic drug, procured through site NHS pharmacy	As per SmPC conditions

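### Each arm's comparator is limited only by calendar time, so it can include, and over-represent, controls who could not have been allocated to that arm

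*Protocol*

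**What the plan says.** Section 7.3 sets the allocation rule: "Participants will be randomised equally to any open arms they are eligible for". Section 7.3.1 has eligibility assessed arm by arm after screening and documented in the notes and the eCRF.

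Section 6.3 lists 18 exclusions for disulfiram and 9 each for dipyridamole and doxycycline. They cover comorbidity, concomitant medication and, for disulfiram, unwillingness to give up alcohol. Each list also has an exclusion by choice, for example "Participant, or investigator objects to randomisation to Disulfiram". Usual care has no such list. Where a drug cannot be supplied, Section 8.6 says that "the site will continue to recruit and randomise participants between the available treatment arms and usual care at that site".

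Section 10.1 then fixes the comparator: "Treatment arm participants will only be compared to contemporaneously recruited control arm participants". It adds "Type I error rate is controlled at 10% for each pairwise comparison". Table 10.1.1 speaks of a shared control, and Section 10.3 of contemporaneous controls. Neither mentions eligibility for the arm. The primary ANCOVA in 10.3 adjusts for baseline log10 NE, the minimisation factors (centre, *Pseudomonas*, long-term macrolides) and further baseline prognostic covariates that are not named.

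**The concern.** Randomisation makes an arm comparable only with controls who could have been allocated to it. A participant with diabetes can be a contemporaneous control for disulfiram but can never be a disulfiram patient. The same holds for an anticoagulated participant and dipyridamole, or for anyone who objected to a given drug. The objection criterion also lets the preference of participant or investigator shape the comparator before allocation.

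The allocation rule makes this worse. Someone barred from one of three open arms has three options instead of four, so is more likely to go to control. If such people differ in day-28 NE after adjustment, the primary contrast mixes the drug effect with that difference. This contrast decides which drugs go forward, and the same rule will apply to every arm added later.

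**Working it through.** **Inputs from the protocol (10.1).** 42 per arm with up to 10% dropout; target difference 0.25 log10; SD 0.5 ("transformed NE is estimated to be 0.5, using unpublished data from the ORBIT4 trial"); one-sided 10% level; up to 4 covariates; R² = 0.1 in the first row of Table 10.1.1; equal concurrent randomisation to control.

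**Inputs not in the protocol (assumptions).** q, the share of participants ineligible for the arm: 20% to 35%. d, the day-28 log10 NE of ineligible minus eligible participants after adjustment: 0 to 0.2 in either direction.

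**1. Reproducing Table 10.1.1.** 42 × 0.9 = 37.8, so take 37 per side. Degrees of freedom are 74 − 2 − 4 = 68 and the critical t is 1.294. The noncentrality is (0.5/√0.9)/√(2/37) = 2.267, multiplied by √B with B ~ Beta(34.5, 2) for four random covariates. Power is 81.8%. The other rows give 85.1%, 88.5% and 91.9%. All four match, so the table assumes a 1:1 comparison.

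**2. Share of controls who could not have received the arm.** With three treatment arms open, the chance of control is 1/4 for someone eligible for all and 1/3 for someone barred from one:

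f = (q/3) / [(1 − q)/4 + q/3]

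- q = 0.20: 0.0667/(0.2000 + 0.0667) = 0.25. For 42 in the arm, about 42/0.75 = 56 controls, 14 of them ineligible.
- q = 0.35: 0.1167/(0.1625 + 0.1167) = 0.418. About 42/0.582 = 72 controls, 30 of them ineligible.

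The shares change as arms open or close, or if people are barred from two arms (chance of control 1/2).

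**3. Bias and error rates.** Bias = f × d. With 37 analysed in the arm and 37/(1 − f) controls, SE = 0.5 × √0.9 × √[1/37 + (1 − f)/37], which is 0.103 at q = 0.20 and 0.098 at q = 0.35. In absolute values, type I error = Φ(bias/SE − 1.2816) when ineligible controls have higher NE. Power = Φ((0.25 − bias)/SE − 1.2816) when they have lower NE.

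| q | size of d | f | bias | type I error (ineligible higher) | power (ineligible lower) |
|---|---|---|---|---|---|
| 0.20 | 0 | 25% | 0 | 10% | 87% |
| 0.20 | 0.1 | 25% | 0.025 | 15% | 82% |
| 0.20 | 0.2 | 25% | 0.050 | 21% | 74% |
| 0.35 | 0 | 42% | 0 | 10% | 90% |
| 0.35 | 0.1 | 42% | 0.042 | 20% | 80% |
| 0.35 | 0.2 | 42% | 0.084 | 33% | 66% |

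With 38 analysed per arm the last row becomes 34% and 67%. On this normal formula, 37 eligible controls against 37 in the arm give 83.8% power. That is the like-for-like benchmark for the last column.

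**4. Check by simulation.** One covariate with R² = 0.1, q = 0.30, 2,500 runs per setting:

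| true effect | d | rejects, all concurrent controls | rejects, eligible concurrent controls |
|---|---|---|---|
| 0 | +0.15 | 22.5% | 9.6% |
| 0 | +0.25 | 33.7% | 8.7% |
| 0.25 | −0.25 | 61.8% | 84.2% |
| 0.25 | 0 | 88.4% | 82.8% |

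The eligible-control estimate stays unbiased whatever d is. Each person eligible for an arm has the same chance of that arm and of control, whatever else is open to them, so the expected ratio is 1:1 (42 against 42).

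**The case against.** The strongest reply is that Section 10.1 states a necessary condition, ruling out historical controls, and does not say that every concurrent control is used. Section 10.3 leaves full details to a separate SAP, which is not at hand and could add the restriction. The 1:1 power calculation also fits an eligible-control comparison. This stands as far as it goes: a reader might infer that the protocol prescribes pooling every control, and it does not say so in those words. But it does state a comparator and claims error control for it, and an SAP that follows that sentence literally would include ineligible controls.

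A reader might also infer that the comparison is not randomised at all, or is known to be biased. The documents support neither. In the illustration, 58% to 75% of the controls are eligible and concurrently randomised. Nothing in the protocol shows that diabetes, alcohol use or objection to a drug predicts sputum NE. All participants must be NEATstik-positive, baseline NE is in the model, and the unnamed prognostic covariates may capture some of the comorbidity. A difference of 0.2 log10 would be 80% of the target effect.

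The site-supply part is weaker. Centre is a minimisation factor and so is in the model, and with a fixed centre term a site that never had the drug adds essentially nothing directly to that contrast. Mainly intermittent supply remains.

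Finally, this is a phase II screen whose signals are to be confirmed. That lowers the stakes, but the protocol still claims 10% per comparison.

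**Conclusion.** The point holds in a limited form. As written, the comparator may contain people who could not have been allocated to the arm, and the allocation rule over-represents them. The comparison is then not fully randomised, and the 10% error rate depends on an unstated condition: equal day-28 NE in eligible and ineligible controls after adjustment.

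Size and direction are unknown. At zero residual difference there is no bias and pooling gains power. Over the assumed ranges with a non-zero difference, the bias is about a tenth to a third of the 0.25 target. Type I error is then about 15% to 34%, or power about 82% to 66%. The 82% end is no loss against the planned 81.8%, although it is slightly below the like-for-like 83.8%. It would be wrong to conclude that Table 10.1.1 is in error: it reproduces exactly and describes the eligible-control comparison.

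The comparator should be settled before any arm is analysed.

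**What to change.** State in 10.1 and repeat in 10.3: *Each treatment arm is compared only with control participants randomised while that arm was open and available at their site, and who were recorded as eligible for that arm at randomisation.* Apply the same set to the primary, secondary and safety comparisons. The analysis with all contemporaneous controls may be kept as a sensitivity analysis.

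The cost is one sentence and one derived variable. Per-arm eligibility is already recorded (7.3.1); the availability of each drug at each site on the day of randomisation must be recorded too. There are fewer controls than with pooling, so some precision is lost if the residual difference is zero (82.8% against 88.4% power in the simulation at 30% ineligible). The expected 1:1 ratio behind Table 10.1.1 is kept, so planned power is unchanged.

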10.1.1. Sample size calculation, sub-study

The sub-study is being carried out for exploratory outcomes only and no sample size calculation is required.

10.2. Planned recruitment rate

Recruitment to the first 3 treatment arms and contemporaneously randomised control arm participants is expected to take approximately 22-30 months across 10 recruiting sites. As treatment arms are added recruitment will continue.

10.3. Statistical analysis plan

The primary analysis will be performed on an intention-to-treat basis. Analysis of covariance (ANCOVA) will be used to compare the log₁₀-transformed NE between the control and each treatment arm after 28 days, with baseline log₁₀-transformed NE included as a covariate in addition to terms for trial arm, minimisation factors and relevant baseline prognostic variables. Missing data will be dealt with using multiple imputation, assuming missing-at-random is an appropriate assumption; methods exploring other mechanisms may be performed as appropriate. The estimated difference between the arms in log₁₀-transformed NE will be presented along with the corresponding 80% confidence interval and 1-sided p-value. Analysis makes a working independence assumption. To account for the re-randomisation of patients, cluster-robust standard errors will be computed (Kahan et al. 2021)

NE over the entire study period will be compared between arms using linear mixed effects models, including fixed effect terms for trial arm, stratification factors and relevant baseline prognostic variables, and a random intercept participant effect. Quality of life outcomes will be compared between arms using a similar approach.

Analysis of time to first exacerbation will be conducted using a Cox regression model incorporating trial arm, stratification factors and relevant baseline prognostic variables. The hazard ratio, 80% CI and 1-sided p-value associated with study arm will be obtained from this model, using cluster-robust standard errors. A Kaplan-Meier plot will be used to illustrate the relative time to first exacerbation in each arm and contemporaneous controls, with proportion of patients exacerbation-free after 28 and 56 days and associated 80% CIs provided.

Safety will be assessed by tabulating AEs that occurred in at least 10% of the safety population participants in either arm; these will be further broken down by severity. Treatment compliance (including number of expected doses taken/missed, number of dose

reductions (if applicable), reasons for missed doses/dose reductions, etc) will be summarised for each treatment arm.

Full details, including planned sensitivity analyses and the approach for handling missing data, will be provided in a separate Statistical Analysis Plan.

